Revision Version	Protocol Date	Template number and version	Protocol Section Modified	Summary of Changes [note: confirm with Reg as to level of detail needed (e.g. verbatim or summary)]	Justification for Modification [note: Include any potential impact on the performance, effectiveness, safety or other endpoints). Please also update the impacted sections of the protocol as applicable.]
Ver A	Oct 28,2021	92120219_R ev/Ver G	NA	NA	Original release
Ver B	Jan 25,2022	92120219_R ev/Ver G	7.1	Add introduction of “association study-SpaceOAR real world study in Hainan’	Based on EC’s opinion
Ver B	Jan 25,2022	92120219_R ev/Ver G	7.2	Add ’The target population in this study are patients diagnosed with localized prostate cancer who took part in SpaceOAR RWS in Hainan (U0720)’.	Based on EC’s opinion
Ver B	Jan 25,2022	92120219_R ev/Ver G	9.2	Modified the wording in ‘study candidates screening’	Based on EC’s opinion
Ver B	Jan 25,2022	92120219_R ev/Ver G	9.4	Add process of SpaceOAR real world study briefly.	Based on EC’s opinion
Ver B	Jan 25,2022	92120219_R ev/Ver G	Cover & Contact Information	PI was changed to [name], and hospital was changed to Shanxi Provincial Cancor hospital	Company Strategy updated

2. Protocol Synopsis

[figure not shown]
An observational study to evaluate the safety and effectiveness of radiotherapy for localized T1-T2 prostate cancer in China after injection of SpaceOAR Hydrogel

An observational study of radiotherapy after injection of SpaceOAR Hydrogel

Study Objective(s)	This observational study aims to evaluate the safety and effectiveness of radiotherapy for subjects with localized T1-T2 prostate cancer in China who were injected with SpaceOAR Hydrogel, via collecting clinical data related to radiotherapy.
Study design	
This study protocol is for the second part of SpaceOAR real world study in which long term follow-up visits will be performed (up to 1 year) outside Boao Medical Tourism Pilot Zone. The SpaceOAR real world study is a retrospective and prospective, single arm, observational study (Protocol of SpaceOAR RWS Windchill#: 92743236). Subjects with localized T1-T2 prostate cancer who have already been injected with the SpaceOAR and have received radiotherapy or will receive radiotherapy will be enrolled, and clinical data related to radiotherapy will be collected.
 
For subjects who have already completed radiotherapy before study kick-off, clinical data will be collected retrospectively, such as data related to radiotherapy, AE (if any) and MRI (if any). Follow up visit will be completed if applicable.
 
For subjects who receive therapy after study kick-off, follow up visits at 2 weeks, 6 weeks, 3 months and 10 months after radiotherapy will be scheduled to assess bowel, urinary and sexual function and quality of life.

An observational study to evaluate the safety and effectiveness of radiotherapy for localized T1-T2 prostate cancer in China after injection of SpaceOAR Hydrogel

An observational study of radiotherapy after injection of SpaceOAR Hydrogel

Space OAR observational Study Design

Planned Number of Subjects	Up to 20 eligible subjects will be enrolled to generate data including 14 subjects at least.
Planned Number of Sites / Countries	1 site, Shanxi Provincial Cancer Hospital

An observational study to evaluate the safety and effectiveness of radiotherapy for localized T1-T2 prostate cancer in China after injection of SpaceOAR Hydrogel

An observational study of radiotherapy after injection of SpaceOAR Hydrogel

Primary Endpoint	
Reduction of dose volume of rectum receiving x Gy as specified below, which is measured from CT simulation scans acquired pre and post SpaceOAR hydrogel injection, that is Vx Gy :
 
• For conventionally fractionated regimen: V70Gy• For moderately hypofractionated regimen: V46Gy, V37Gy• For ultrahypofractionated regimen: V29 Gy, V18. 1 Gy, V36 Gy 
Dose to the anterior rectum is quantified by computing a rectal dose-volume histogram (DVH).

Second Endpoints	
1. EPIC bowel and urinary assessment composite score at 2 weeks, 6 weeks, and 3 months post radiotherapy2. EPIC sexual assessment composite score at 2 weeks, 6 weeks, and 3 months post radiotherapy3. Quality of Life at 2 weeks, 6 weeks, and 3 months post radiotherapy (QOL)4. Whether there is SpaceOAR hydrogel between the posterior prostatic capsule and the anterior rectal wall at 6 weeks post radiotherapy.5. Whether the SpaceOAR hydrogel between the prostate and the anterior rectal wall is absorbed in 10 months post radiotherapy.6. Rectal adverse event (CTCAE)7. AEs/SAEs related to SpaceOAR hydrogel
Follow-up Schedule	Follow ups at 2 weeks, 6 weeks, 3 months, and 10 months after radiotherapy will be scheduled prospectively, if applicable.
Study Duration	The total study duration is estimated to be approximately 15 months.
Participant Duration	The study duration for subject enrolled prospectively is expected to be approximately 12 months.
Inclusion Criteria	
• Subjects have provided the written informed consent, are willing to participate in clinical data collection and willing to comply with study procedure. (for subjects enrolled prospectively)

An observational study to evaluate the safety and effectiveness of radiotherapy for localized T1-T2 prostate cancer in China after injection of SpaceOAR Hydrogel

An observational study of radiotherapy after injection of SpaceOAR Hydrogel

	
Subjects must have been pathologically confirmed prostate cancer with clinical stage T1-T2, and have been treated with Space OAR Hydrogel, and have received or will receive radiotherapy.
Exclusion Criteria	This is an observational study, all subjects have received radiotherapy or will receive radiotherapy, who have injected with SpaceOAR hydrogel in Boao Medical Pilot Zone. There is no specific exclusion criteria unless the patients refuse to sign the informed consent.
Statistical Methods	
Statistical Hypothesis	There are no hypotheses for this second stage of the SpaceOAR Real World study. All the endpoints are descriptive in nature.
Statistical Test Method	Descriptive statistics will be used to summarize the study endpoints, which include, but not limited to, dose volume of rectum receiving x Gy, EPIC composite score, and AEs. Continuous variables will be tabulated with mean, median, standard deviation, minimum, maximum, when appropriate. Categorical variables be tabulated with frequencies, percentages along with the 95% confidence intervals when appropriate. There is no formal interim analysis, but a descriptive summary of the study data may be made during the study, if needed.

3. Table of Contents

1. TITLE PAGE	1
2. PROTOCOL SYNOPSIS.....	5
3. TABLE OF CONTENTS.....	9
3.1. Table of Figures	11
3.2. Table of Tables.....	12
4. INTRODUCTION	13
4.1. Background	13
4.2. Study Rationale	15
5. STUDY OBJECTIVES AND ENDPOINTS.....	15
5.1. Study Objectives	15
5.2. Study endpoints	15
6. STUDY DESIGN	16
6.1. Scale and Duration	17
6.2. Treatment Assignment	17
6.3. Justification for the Study Design	18
6.4. Method to reduce biases.....	18
7. SUBJECT SELECTION	18
7.1. Association study-SpaceOAR Real World Study in Hainan (U0720)	18
7.2. Study Population and Eligibility	18
7.3. Inclusion Criteria.....	19
7.4. Exclusion Criteria.....	19
8. SUBJECT ACCOUNTABILITY	19
8.1. Point of Enrollment.....	19
8.2. Withdrawal.....	19
8.3. Lost to Follow-Up	19
8.4. End-of-Study Definition.....	20
9. STUDY METHODS	20
9.1. Data Collection.....	20

9.2. Study Candidate Screening	20
9.3. Informed Consent.....	20
9.4. study visits.....	21
9.5. Study Completion.....	22
9.6. Source Documents	22
10. STATISTICAL CONSIDERATIONS	22
10.1. Study hypotheses.....	22
10.2. General Statistical Methods	23
10.3. Data Analyses.....	23
11. DATA MANAGEMENT	24
11.1. Data Collection, Processing, and Review	24
11.2. Data Retention.....	24
12. AMENDMENT	25
13. DEVIATIONS	25
14. COMPLIANCE	25
14.1. Statement of Compliance	25
14.2. Investigator Responsibilities	26
14.3. Institutional Review Board/ Ethics Committee.....	28
14.4. Sponsor Responsibilities	28
14.5. Insurance	29
15. MONITORING	29
16. POTENTIAL RISKS AND BENEFITS	29
16.1. Anticipated Adverse Events and Anticipated Adverse Device Effects of SpaceOAR system.....	29
16.2. Risks associated with Participation in the Clinical Study	30
16.3. Risk Minimization Actions	30
16.4. Anticipated Benefits	30
17. SAFETY REPORTING.....	31
17.1. Reportable Events by investigational site to Boston Scientific	31
17.2. Definitions and Classification	31

Reported prostate cancer incidence has increased with introduction of the prostate-specific antigen (PSA) blood test. Application of the PSA test has allowed for earlier detection of prostate cancer and earlier intervention such that disease-specific mortality rates have declined⁵. Treatment options for prostate cancer include surgical resection (radical prostatectomy), radiation (brachytherapy (BT) or external beam radiotherapy (EBRT)), cryotherapy, hormonal therapy (androgen deprivation) or “watchful waiting”/active surveillance involving no immediate treatment but yearly or biannual biopsies or medical monitoring. The choice of treatment is based on a multidisciplinary approach, taking into account tumor staging, Gleason score, baseline PSA, patient age, comorbidity, life expectancy and quality of life. In localized prostate cancer (i.e. T1c-T2c), external radiation therapy is commonly recommended, particularly for young patients who refuse surgical intervention or for patients who are not good surgical candidates⁶. An increasing number of men choose radiotherapy for the treatment of localized prostate cancer because of the perception that there is a lower risk of impotence and incontinence⁷.

Although each of the treatment options have associated risks and benefits, one of the more significant concerns associated with radiation therapy (RT) is the potential for acute and late rectal injuries caused by direct mucosal damage from ionizing radiation. Acute radiation gastrointestinal (GI) injury is typically characterized as that which occurs during and within the immediate twelve weeks after completion of therapy. Toxicity can be manifested as diarrhea, pain, a sense of rectal distention with cramping, rectal urgency or tenesmus, mucous production and bleeding. Occasionally, superficial ulceration causes bleeding that may require endoscopic cauterization or medical therapy for anemia including transfusion^{8,9}. Late effects include rectal dysfunction requiring surgical intervention, necrosis, perforation and life threatening bleeding. Late toxicity is attributable to progressive epithelial atrophy and fibrosis associated with obliterative endarteritis and chronic mucosal ischemia^{10,11}.

Symptoms usually are persistent in nature, and may take up to 6-12 months to appear but can occur any time post-irradiation up to 30 years after exposure^{10, 12}. Of note, several researchers have documented a positive correlation between acute and late GI toxicity demonstrating that late complications are more likely to occur in patients who also experienced acute complications^{8,9,13,14}.

There have been several advancements in the delivery of external beam radiotherapy (EBRT) including improvement in accelerator equipment used for the delivery of RT, improved

imaging and planning algorithms, and target localization through the use of Image Guided Radiotherapy (IGRT). Despite the improvements in RT delivery, acute and chronic gastrointestinal toxicity remains a concern. With dose-escalation (e.g., ≥ 78 Gy), rates of acute and chronic Grade ≥ 2 rectal toxicity associated with Intensity Modulated Radiation Therapy (IMRT), the most contemporary form of RT, have been documented to range from 3-50% and 5-24%, respectively^{15,20}.

It is well documented that the volume of normal rectal tissue exposed to varying radiation dose levels represents the most significant factor affecting the development of acute and late rectal toxicity^{11,15-29}. Specifically, it has been noted that patients with greater than 25% of the rectum irradiated to 70 Gy had a significantly higher risk of developing Grade 2 or higher rectal toxicity scored using physician reported toxicity RTOG criteria for GI toxicity. Furthermore, all Grade 3 complications occurred when greater than 30% of the rectum received ≥ 70 Gy¹¹. Other rectal dose metrics have also been qualified as a risk factor for late gastrointestinal symptoms.

Although traditionally GI toxicity has been evaluated based on the physician's assessment, recently there has been a transition to change focus to patient-reported outcomes using detailed quality of life analysis. When evaluating toxicity from a patients' perspective, IMRT has an associated acute and late GI toxicity that has been demonstrated to have an important impact on quality of life¹⁴. A patient self-assessment questionnaire analysis performed by Koper et al., revealed that soiling and fecal loss (both surrogates for fecal incontinence) and mucus discharge were the most bothering complaints and of greater patient concern than rectal bleeding²¹. In a study published by Sanda et al, radiotherapy was associated with a reduced quality of life related to bowel function early after treatment, and the change lasted for a year or more. Rectal urgency, frequency, pain, fecal incontinence, or hematochezia caused distress related to bowel function in 9% of patients one year after radiotherapy and moderate to severe (i.e., "big") bowel and rectal function was reported in 11% of patients evaluated²². These studies lead to the conclusion that non-physician scored toxicity criteria (i.e., parameters not necessarily considered when applying the RTOG toxicity criteria) have a substantial impact on quality of life. Consistent with physician-scored toxicity, increased rectal doses has been demonstrated to have a significant negative impact on patient reported bowel quality of life (QOL)²³ and early quality of life has been reported to be a strong predictor of later QOL²⁴. Therefore, technologies that can minimize rectal exposure to incidental radiation would represent an important tool in modern EBRT therapy.

The SpaceOAR System is an in-situ formed absorbable hydrogel that is administered transperineally (with transrectal ultrasound guidance) between the prostate and rectum (posterior to Denonvilliers' fascia and anterior to the fascia propria of the rectum). The formed hydrogel displaces the rectum away from the prostate during prostate radiotherapy and thereby has the potential to reduce rectal wall/mucosa radiation exposure. The SpaceOAR hydrogel material is designed to maintain rectal displacement away from the prostate for three months ensuring a stable relationship between the prostate and rectum during the typical nine week radiotherapy protocol. SpaceOAR hydrogel then slowly absorbs via hydrolysis and is cleared from the implant site in approximately six months. It's well documented that the volume of rectum was reduced during radiotherapy when the SpaceOAR System is used as a means to physically separate the rectum from the prostate in previous

studys^{25,26}. The 3 year incidence of grade 1+ and grade 2+ rectal toxicity was reported to reduce significantly when the spaceOAR were used in follow up study (2% vs 9.2%, 0% vs 5.7%)²⁶.

4.2. *Study Rationale*

The SpaceOAR System is designed to create space between the rectum and prostate to reduce rectal wall/mucosa radiation exposure during prostate radiotherapy, then reduces the rectal damage. This medical device has been marketed in US, Europe and many other countries, and its safety and effectiveness have been confirmed in the previous studies in radiotherapy for prostate cancer, and Incidence of grade 1+ and grade 2+ rectal toxicity reduced significantly.

The SpaceOAR System is an advanced medical device, and there is no similar device in China. In accordance with the policy on special innovative medical devices, SpaceOAR can be used in clinical practice as a special innovative medical device in The Boao Lecang Medical Pilot Zone in Hainan. This study will collect relevant clinical data of Chinese patients who received radiotherapy after SpaceOAR hydrogel is administrated, to evaluate its safety and performance during radiotherapy in a real world setting.

5. Study Objectives and Endpoints

5.1. *Study Objectives*

This observational study aims to evaluate the safety and effectiveness of radiotherapy for subjects with localized T1-T2 prostate cancer in China who were injected with SpaceOAR Hydrogel, via collecting clinical data related to radiotherapy.

5.2. *Study endpoints*

5.2.1. Primary endpoint

Reduction of dose volume of rectum receiving x Gy as specified below, which is measured from CT simulation scans acquired pre and post SpaceOAR hydrogel injection(i.e.Vx Gy):

- For conventionally fractionated regimen: V70Gy
- For moderately hypofractionated regimen: V46Gy, V37Gy
- For ultrahypofractionated regimen: V29 Gy, V18. 1 Gy, V36 Gy

Dose to the anterior rectum is quantified by computing a rectal dose-volume histogram (DVH).

5.2.2. Second endpoints

1. EPIC bowel and urinary Assessment composite score at 2 weeks, 6 weeks and 3 months post radiotherapy

2. EPIC Sexual Assessment composite score at 2 weeks, 6 weeks, and 3 months post radiotherapy
3. Quality of Life at 2 weeks, 6 weeks and 3 months post radiotherapy (QOL)
4. Whether there is SpaceOAR hydrogel between the posterior prostatic capsule and the anterior rectal wall at 6 weeks post radiotherapy.
5. Whether the SpaceOAR hydrogel between the prostate and the anterior rectal wall is absorbed in 10 months post radiotherapy.
6. Rectal adverse event (CTCAE)
7. AEs/SAEs related to SpaceOAR hydrogel

6. Study Design

The SpaceOAR real world study is a retrospective and prospective, single arm study, and this study protocol is for the second part of the SpaceOAR real world study in which long term follow-up will be performed (up to 1 year) outside Boao Medical Tourism Pilot Zone. Subjects with localized T1-T2 prostate cancer who have already been injected with the SpaceOAR and have received radiotherapy or will receive radiotherapy will be enrolled, and clinical data related to radiotherapy will be collected.

For subjects who have already completed radiotherapy before study kick-off, clinical data will be collected retrospectively, such as data related to radiotherapy, AE (if any) and MRI (if any), and follow up will be performed, if applicable.

For subjects who receive therapy after study kick-off, radiotherapy relevant clinical data will be collected, and follow up visits after radiotherapy will be scheduled to assess urinary, bowel, sexual functions and AE.

All administration of SpaceOAR hydrogel will be completed by trained urologists in the hospital in Boao.

All radiotherapy planning will be made according to clinical practice and stage of Pca at discretion of the doctors.

[figure not shown]

Figure 6-1 Space OAR observational Study Design

6.1. Scale and Duration

Up to 20 subjects with localized Pca will be enrolled in this study and followed by radiotherapy after injection of SpaceOAR. This study is based on the use of special medical device in Hainan BOAO medical tourism pilot zone, the enrollment may be slow due to limited patient pool. Together, the study enrollment, radiotherapy, and follow up visits are expected to be completed in 15 months.

6.2. Treatment Assignment

This is a single arm, observational study without treatment assignment. All subjects receive radiotherapy in sites when they were treated with SpaceOAR hydrogel at the hospital in Hainan BOAO.

6.3. *Justification for the Study Design*

SpaceOAR system has been firstly used in Hainan BOAO as a special medical device, while there is no evidence about the radiotherapy after SpaceOAR hydrogel injection in China. As a result, an observational study is conducted to gather the relevant clinical data in Chinese patients with localized PCa who receive radiotherapy after SpaceOAR hydrogel is injected. Due to limited patient pool in BOAO, the subjects will be enrolled prospectively and retrospectively to speed up the study recruitment..

6.4. *Method to reduce biases*

To reduce bias of primary endpoints, objective endpoints, Vx Gy, are used. They are obtained by computing a rectal dose-volume histogram (DVH) in the same hospital.

7. Subject Selection

7.1. *Association study-SpaceOAR Real World Study in Hainan (U0720)*

SpaceOAR Real World Study is conducted based on the use of special medical devices in the Boao Lecheng Medical Pilot Zone in Hainan. Patients who have been diagnosed with stage T1-T2 prostate cancer and are scheduled to receive radiation therapy will be recommended to participate in the SpaceOAR RWS after informed consent is done fully. If patients voluntarily participate in the study, they can go Boao Yiling Life Care Center in Hainan to receive SpaceOAR gel injection.

The injection of SpaceOAR hydrogel is performed by trained urologists, via rectal ultrasound guided under general anesthesia or local anesthesia and sedation. Subjects will go back Local hospital, where simulated mapping CT and MRI examination will be performed to make radiotherapy treatment plan in time post-discharge (Shanxi Provincial Cancer Hospital is recommended).

Subjects will be called by phone at 30 days after discharge to collect adverse events and Device Deficiency (if applicable) to assess patient health. The relevant clinical data generated in another hospital (e.g., Local hospital where subjects have been examined) will be collected when applicable.

In addition, the study will retrospectively collect the clinical data of patients who had completed SpaceOAR hydrogel injection before the study kick-off.

7.2. *Study Population and Eligibility*

The target population in this study are patients diagnosed with localized prostate cancer who took part in SpaceOAR RWS in Hainan (U0720) and have been treated with SpaceOAR Hydrogel in hospital in Hainan Boao, are receive or will receive radiotherapy in this site.

7.3. *Inclusion Criteria*

Subjects who meet all the following criteria may be given consideration for inclusion in this clinical investigation, provided no exclusion criterion is met.

- Subjects have provided the written informed consent, are willing to participate in clinical data collection and willing to comply with study procedure. (for subjects enrolled prospectively)
- Subjects must have been pathologically confirmed prostate cancer with clinical stage T1-T2, and have been treated with Space OAR Hydrogel, and have received or will receive radiotherapy.

7.4. *Exclusion Criteria*

There are no specific exclusion criteria unless the patients refuse to sign the informed consent.

8. Subject Accountability

8.1. *Point of Enrollment*

During screening, patients who have received or will receive radiotherapy will be identified. These who have been injected with SpaceOAR hydrogel will be enrolled. For patients who have already received radiotherapy, the clinical data can be collected retrospectively, and informed consent will be performed (If follow up visits can be conducted prospectively). For patients who will receive radiotherapy, informed consent will be gained.

8.2. *Withdrawal*

All subjects enrolled in the clinical study (including those withdrawn from the clinical study) shall be accounted for and documented. If a subject withdraws from the clinical investigation, the reason(s) shall be reported. The applicable CRF(s), including the end of the study form, shall be completed at the time of subject withdrawal.

8.3. *Lost to Follow-Up*

A subject will be considered lost to follow-up if he fails to complete 30 days follow-up visits and is unable to be contacted by the study site staff after at least three documented attempts, at which point an End of Study form should be completed. Before a participant is deemed lost to follow up, the investigator or designee will make every effort to regain contact with the participant (where possible, 3 telephone calls and, if necessary, a certified letter to the participant's last known mailing address or local equivalent methods). These contact attempts should be documented in the participant's medical record or study file. (only for patients enrolled prospectively).

8.4. *End-of-Study Definition*

A subject is considered to have completed the study if he has completed all phases of study including the last visit or last scheduled procedure shown in the data collection schedule.

A clinical trial is considered completed when participants are no longer being examined or the last participant's last study visit has occurred.

9. Study Methods

9.1. *Data Collection*

The data collection schedule is shown in Table 9-1.

Table 9-1: Data Collection Schedule

Procedure/Assessment	Before RT	RT	After RT			
			2W (\pm 3days)	6W (\pm 7days)	3M (\pm 15days)	10M (\pm 30 days)
Informed consent	X					
PSA	X			X		X
CT	X*					
MRI	X*			X		X
Radiotherapy		X				
EPIC questionnaire	X		X	X	X	
EQ-5D-5L questionnaire	X		X	X	X	
Concomitant medication	X	X	X	X	X	X
Adverse event	X	X	X	X	X	X
Protocol Deviation	X	X	X	X	X	X
Device Deficiency[#]	X	X	X	X	X	X

NOTE:1. Data at baseline such as demography, medical history, Pca, etc. refer to SpaceOAR RWS (U0720).
 2.*CT&MRI for mapping, which used to make RT planning, 2 times.
 3.# DD of Space OAR hydrogel.

9.2. *Study Candidate Screening*

Patients diagnosed with localized prostate cancer who have been injected with SpaceOAR hydrogel in SpaceOAR RWS in Hainan (U0720) will be invited to participate in this study.

9.3. *Informed Consent*

For patients who receive radiotherapy after SpaceOAR injected, investigator will introduce study information to subject and get ICF. Once the ICF is signed, he is enrolled in study. If he fails to receive radiotherapy after ICF signed, the subjects are screening failure.

9.4. *study visits*

The subject of SpaceOAR RWS are going to participate in this study when he completed last visit. the process of SpaceOAR RWS is summarized below.

- Patients who diagnosed with T1-T2 prostate cancer and scheduled to receive RT will be screened and recommended to participate in SpaceOAR RWS in Hainan. After informed consent is done fully, Mapping CT and MRI will be conducted. (Shanxi Provincial Cancer Hospital is preferred.)
- Subjects go to Boao Yiling Life Care Center in Hainan to receive SpaceOAR gel injection voluntarily, which is completed by trained and qualified urologist.
- After discharge, subjects will receive Mapping CT and MRI to make RT plan, then receive RT. (Shanxi Provincial Cancer Hospital is preferred, i.e., enrolled in this study)
- At 30 days after SpaceOAR injection, a phone visit will be completed. Then subject complete all visits.

Subjects who have been injected with SpaceOAR in Hainan BOAO return to participate in this observational study. subjects receive radiotherapy per site's clinical practice, then will be followed in 2 weeks, 6 weeks, 3 months and 10 month after RT.

1) Before RT

RT planning before and after SpaceOAR hydrogel injection will be made (such as planning type of EBRT, planning RT regimen, CTV, PTV and constraint of risk organs, etc.). The RT planning of the subjects will be determined by the investigators based on the current clinical practice and PCa staging and conditions of the subjects.

The questionaries of EPIC and EQ-5D-5L will be completed, adverse event and Device Deficiency (if applicable) will be assessed and collected.

Note: The subject's demographic, medical history, genitourinary history, prostate treatment, PCa therapies, PCa staging, Gleason score, etc., are collected in the SpaceOAR RWS(U0720).

2) RT

RT is conducted according to RT planning after SpaceOAR injection; adverse event and Device Deficiency will be collected, if applicable.

3) Follow-ups after RT

2 weeks post RT: the questionaries of EPIC and EQ-5D-5L will be completed to assess the functions of urinary, rectum and health related Quality of life; Adverse event and Device Deficiency will be collected, if applicable.

6 weeks post RT: the questionaries of EPIC and EQ-5D-5L will be completed to assess the functions of urinary, rectum and health related Quality of life; Adverse event and Device Deficiency will be collected, if applicable; MRI will be performed.

3 months post RT: the questionaries of EPIC and EQ-5D-5L will be completed to assess the functions of urinary, rectum and health related Quality of life; Adverse event and Device Deficiency will be collected, if applicable.

10 months post RT: MRI will be performed; Adverse event and Device Deficiency will be collected, if applicable.

NOTE: For subjects who have received RT (after SpaceOAR injection), applicable follow up will be performed after participation in this study to assess adverse event and device deficiency, if any, then to collect clinical data. The clinical data before participation will be collected retrospectively at same time.

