17.1. Reportable Events by investigational site to Boston Scientific

It is the responsibility of the investigator to assess and report to BSC any event which occurs in any of following categories:

- All adverse events
- All serious adverse events
- All Adverse Events related to Study Device
- All Serious Adverse Events related to Study Device
- All Adverse Events related to RT
- All Serious Adverse Events related to RT
- Unanticipated Adverse Device Effects/Unanticipated Serious Adverse Device Effects
- All Device Deficiencies
- New findings/updates in relation to already reported events

When possible, the medical diagnosis should be reported as the Event Term instead of individual symptoms.

If it is unclear whether an event fits one of the above categories, or if the event cannot be isolated from the device or procedure, it should be submitted as an adverse event and/or device deficiency.

Any reportable event, experienced by the study subject after informed consent, whether prior to, during or after RT, must be recorded in the eCRF.

Underlying diseases and chronic conditions are not reported as AEs unless there is an increase in severity or frequency during the investigation. Death should not be recorded as an AE, but should only be reflected as an outcome of one (1) specific SAE (see Table 17-1 for AE definitions).

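### Protocol 9.4 is inconsistent on when a prospective subject enters the study, so the pre-radiotherapy EPIC and EQ-5D-5L may fall before consent and go uncollected

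*Protocol*

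**What the plan says.** **Entry after the parent study's last visit.** Protocol 9.4 opens with "The subject of SpaceOAR RWS are going to participate in this study when he completed last visit". Its summary of U0720 ends with "At 30 days after SpaceOAR injection, a phone visit will be completed. Then subject complete all visits". Read together, these start participation after the 30-day call.

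**Entry at planning or consent.** Other text, some of it in the same section, gives no such wait:

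- Protocol 9.4, third step of the U0720 summary: "After discharge, subjects will receive Mapping CT and MRI to make RT plan, then receive RT", followed by the remark "Shanxi Provincial Cancer Hospital is preferred, i.e., enrolled in this study".
- Protocol 9.4, after the summary: injected subjects come back to join this study and then have RT.
- Protocol 8.1: consent is obtained from patients who are still to receive RT.
- Protocol 9.2: patients "injected with SpaceOAR hydrogel in SpaceOAR RWS in Hainan (U0720) will be invited to participate in this study".
- Protocol 9.3: "Once the ICF is signed, he is enrolled in study".
- Table 9-1: consent, PSA, EPIC and EQ-5D-5L all stand in the column before RT.
- Protocol section 18: for prospective subjects, consent precedes study procedures and data collection.

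**What is due before RT.** Protocol 9.4 says, for that visit: "The questionaries of EPIC and EQ-5D-5L will be completed, adverse event and Device Deficiency (if applicable) will be assessed and collected". Note 1 to Table 9-1 takes demography, history and cancer data from U0720. The note in 9.4 adds items such as staging and Gleason score. Neither names EPIC or EQ-5D-5L.

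**Use in the analysis.** SAP 5.2.1 summarises baseline EPIC and EQ-5D-5L. SAP 3.2.2 plans a paired t-test or Wilcoxon signed-rank test for before-and-after assessments.

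**Adverse events.** Protocol 17.1 requires recording of "Any reportable event, experienced by the study subject after informed consent".

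**The concern.** A site that takes the opening sentence of 9.4 as its instruction would wait for the 30-day call before approaching the subject. If RT has begun by then, Table 9-1 can no longer be met: the questionnaires due before RT would have had to be completed before consent, which section 18 does not allow for prospective subjects.

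A patient-reported score from before treatment cannot be recovered from a chart. Without it, the EPIC and EQ-5D-5L results at 2 weeks, 6 weeks and 3 months have no within-subject reference in a single-arm study of 14 to 20 men. The protocol also gives no warning signal if a site classes such a subject's earlier data as retrospective, because section 13 does not count missing retrospective data as deviations.

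**Working it through.** No stated figure needs reproducing: the SAP has no sample size calculation and the point concerns visit order. The check asks whether RT before the call is possible on the documents' own figures, and what a lost baseline would cost.

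**1. Is an RT start before day 30 plausible?** The documents give no start day. Protocol 4.1 says the hydrogel is designed to hold displacement for three months and calls a nine-week course typical. Taking a month as 30.4375 days and counting from injection:

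3 × 30.4375 − 9 × 7 = 91.3 − 63 = about 28 days.

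A nine-week course lying wholly within that span would start by about day 28, before the call. Both inputs are rounded and shorter regimens leave more room. This shows that the overlap can occur. It is not a schedule and implies no view on when RT should start.

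**2. How much RT would precede entry at day 30?** RT days before entry = min(course length, max(0, 30 − start day)). The start days are assumptions.

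| RT start day (assumed) | RT days before entry, 63-day course | Share of course |
|---|---|---|
| 7 | 23 | 37% |
| 14 | 16 | 25% |
| 21 | 9 | 14% |
| 28 | 2 | 3% |
| 30 or later | 0 | 0% |

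The ultrahypofractionated regimen is also in scope, but its length is not given. If a course of 10 to 14 days is assumed, a start on day 7 or 14 ends by day 28 at the latest (14 + 14), so all of it precedes the call. In every row with a start before day 30, the pre-RT questionnaires fall before consent.

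**3. Does the stated participant duration settle the reading?** Entry at RT start gives (63 + 10 × 30.4375) / 30.4375 = 12.1 months. Entry at day 30 with RT from day 7 to day 70 gives (40 + 304.4) / 30.4375 = 11.3 months. The protocol says about 12 months. Either value could be rounded to that, so the duration does not decide the matter.

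**4. What does a lost baseline cost?** The half-width of the 95% confidence interval for a mean paired change, in SD units of the change, is t(0.975, n − 1) / √n.

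| Usable pairs | Half-width (SD) |
|---|---|
| 20 | 0.47 |
| 14 | 0.58 |
| 10 | 0.72 |
| 7 | 0.92 |

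**5. Can imputation repair it?** SAP 4.3 names LOCF and visit-wise means. LOCF has no earlier value to carry into a missing baseline. A visit-wise mean would insert the average of the other subjects, which contains nothing about the subject concerned.

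**The case against.** The strongest reply is that the opening sentence of 9.4 merely introduces a summary of U0720, and that the sections which govern entry (8.1, 9.2, 9.3, Table 9-1, section 18) agree on consent before RT. A reader might infer from 9.4 that subjects may join only after the 30-day call. The documents do not support that as a settled rule. What stands is an inconsistency, with most of the text on the side of earlier entry.

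A reader might also infer that RT is scheduled before the call because its step is listed first. It is not. The step carries no day, and a nine-week course (63 days) could not be finished before a day-30 call, so the list is not strict chronology.

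A third tempting inference is that early adverse events are lost. Mostly they are not:

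- The U0720 call exists to collect adverse events and device deficiencies (Protocol 7.1).
- The note closing 9.4 collects earlier data retrospectively for subjects who have received RT.
- Table 17-3 gives the site 5 business days for retrospectively collected unanticipated device effects, serious events and device deficiencies.
- Protocol 17.6 gives the sponsor 10 working days for retrospectively collected serious events and for deficiencies that may lead to one.
- Some interval between injection and consent exists under any entry rule, because subjects are injected before they join.

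Two small gaps remain. No passage says that U0720 events enter this study's dataset, and the note in 9.4 does not clearly cover a subject who is mid-course at entry.

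Finally, endpoints 1 to 3 are scores at the visits, not changes from baseline, and the study is descriptive. They can be reported without a baseline. The baseline summary and the paired comparisons cannot.

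**Conclusion.** The point holds as an inconsistency in Protocol 9.4 with a conditional consequence. The condition has two parts: a site follows the opening sentence, and RT starts before day 30. For a subject who meets both, consented pre-RT EPIC and EQ-5D-5L are unobtainable, and he drops out of the observed baseline summary and the before/after comparisons. The share affected is unknown and could be none. If half of 20 subjects were affected, the half-width for a mean change would rise from 0.47 to 0.72 SD.

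The loss is confined to the two questionnaires, and to PSA if it was not measured in routine care. It should not be read as loss of the whole pre-RT baseline: planning CT and dose-volume data for the primary endpoint are clinical records and can be retrieved later.

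This rests on two assumptions: that U0720 does not itself collect EPIC or EQ-5D-5L (its protocol is not available here, and these documents do not name them as transferred), and that the SAP's before-and-after tests use the pre-RT score as the before value.

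The correction is worth making because it is cheap and decides whether data that cannot be recovered are collected.

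**What to change.** Reword the opening sentence of Protocol 9.4 to agree with 8.1, 9.3 and Table 9-1. For example: *Prospective subjects may consent to this study after hydrogel injection. Consent, EPIC and EQ-5D-5L are completed before the first RT fraction, whether or not the 30-day U0720 call has taken place.* RT timing stays with site practice.

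Two secondary clarifications belong in the same amendment:

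- Reconcile the timing of the call, which is 30 days after discharge in 7.1 but 30 days after injection in 9.4.
- State whether hydrogel-related events recorded in U0720 before consent count towards endpoint 7, and how subjects who are mid-course at entry are handled.

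The cost is one protocol sentence and two short clarifications, with ethics committee approval of the amendment and acknowledgement that participation in the two studies may overlap. The U0720 protocol should be checked for any bar on overlap. If U0720 events are to be counted, a data-transfer line is also needed. No treatment or visit changes.

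If enrolment has already closed, the text can no longer alter collection. The report should then state how many subjects had EPIC and EQ-5D-5L completed after consent and before the first fraction, and give that number as the denominator of each before/after comparison.
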